7.4.2 Premedication Other than Dexamethasone for Hypersensitivity Reactions

A by-subject listing of pre-medication for elotuzumab, other than dexamethasone, will be provided. This listing will be generated from the “Pre-medication for Elotuzumab (other than Dexamethasone)” eCRF module and pre-medications will be coded using the BMS WHO drug dictionary.

7.4.3 Concomitant Medication

Concomitant medications are medications, other than study medication or pre-medications for elotuzumab recorded on the “Pre

-medication for Elotuzumab” eCRF page, which are taken by subjects any time on-study, no earlier than the first day of study drug and no later than 60 days after the last dose of study drug. Concomitant medications will be coded using the BMS WHO drug dictionary. If there is clear evidence to suggest that the medication stopped prior to the first dose of study medication, the medication will be assumed to be Prior only.

The number and percentage of subjects taking any concomitant medication and each medication (Anatomical Therapeutic Chemical [ATC] classification system drug name) will be summarized, overall and by treatment group.

A by subject listing of concomitant medication will be provided.

7.4.4 Discontinuation of Study Therapy

The number and percentage of subjects who have discontinued all study treatment and reason for discontinuation will be summarized by treatment group and overall using subject status eCRF page from end of treatment. This summary, unlike other safety analyses, will include all randomized subjects and will be grouped by treatment group as randomized. This is done in order to give a full accounting of all subjects who are off study treatment, including those who were randomized but never treated.

In addition, for subjects in the Elotuzumab arm, who discontinued one drug, while continuing at least one of the other two study drugs, their reason for treatment discontinuation will be summarized based on the dose modification CRF. Subjects will be counted in this summary if there is evidence from the dosing CRF that the subject received the combination therapy in at least one cycle, followed by additional cycles, where one of the drugs in the combination was discontinued.

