3.5 Discontinuation of Subjects followings any Treatment with Study Drug

Subjects MUST discontinue investigational product (and non-investigational product at the discretion of the investigator) for any of the following reasons:

- Subject's request to stop study treatment
- Any clinical adverse event (AE), laboratory abnormality or intercurrent illness which, in the opinion of the investigator, indicates that continued participation in the study is not in the best interest of the subject
- Pregnancy (Subject must discontinue elotuzumab and lenalidomide).
- Termination of the study by Bristol-Myers Squibb (BMS)
- Loss of ability to freely provide consent through imprisonment or involuntarily incarceration for treatment of either a psychiatric or physical (eg, infectious disease) illness
- Progressive Disease (see [Section 5.5.4](#) for definition of disease progression).
- Subjects who receive any non-protocol specified systemic anti-myeloma therapy prior to documented progression will be discontinued from all study treatment (including lenalidomide/dexamethasone), however, tumor assessments must continue at 4 week intervals until documented progression.
- Subjects experiencing a Grade 4 infusion reaction must discontinue elotuzumab. Subjects may continue lenalidomide and dexamethasone treatment. Refer to [Section 4.5.2.2](#).

- Subjects experiencing angioedema, Grade 4 rash, exfoliative or bullous rash, Stevens Johnson syndrome, or toxic epidermal necrolysis related to lenalidomide must discontinue lenalidomide. Subjects in the elotuzumab arm may continue elotuzumab and dexamethasone.
- Subjects experiencing a 28-day delay in all study drugs lenalidomide, dexamethasone, and elotuzumab due to an adverse event(s) related to study treatment must be discontinued from study drug. Subjects experiencing delays unrelated to study therapy, for example due to radiation therapy may delay study treatment up to 42 days. Delays greater than 28 days must be discussed with the medical monitor.

In the case of pregnancy, the investigator must immediately notify the BMS Medical Monitor/designee of this event. In most cases, the study drug will be permanently discontinued in an appropriate manner. If the investigator determines a possible favorable benefit/risk ratio that warrants continuation of study drug, a discussion between the investigator and the BMS Medical Monitor/designee must occur.

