4.5.3 Dose Delay or Interruption

If the dose of one drug in the regimen (ie, lenalidomide, dexamethasone or elotuzumab) is delayed or interrupted, the treatment with the other drugs may continue as scheduled. Subjects experiencing a 28-day delay in all study drugs lenalidomide, dexamethasone, and elotuzumab due to an adverse event(s) related to study treatment must be discontinued from study drug. Subjects experiencing delays unrelated to study therapy, for example due to radiation therapy may delay study treatment up to 42 days. Delays greater than 28 days must be discussed with the medical monitor.

Each cycle is 28 days. While dose delays or interruptions are permitted, the start of each cycle cannot be delayed and is fixed relative to Cycle 1 Day 1. Adjustments to the Cycle 1 Day 1 anchored schedule should not be performed. Missed doses should be skipped, not delayed, if not given within the allowed window.

Subjects may continue on study therapy even if components of the study therapy must be discontinued. For example, a subject on lenalidomide and dexamethasone may continue on study therapy even if dexamethasone must be discontinued for an adverse event. Likewise, a subject on

the investigational arm may continue on study therapy if elotuzumab must be discontinued for an adverse event or other reason. Patients are considered still on study therapy even if they continue solely on lenalidomide.

Please consult the BMS medical monitor or any questions regarding dose interruption or study therapy discontinuation.

4.5.3.1 *Elotuzumab*

In Cycle 1 and 2, an elotuzumab dose that falls outside of the pre-specified window (-1 to +3 days) must be skipped.

In Cycles 3 and beyond, elotuzumab dosing may be delayed for up to 1 week. If unable to administer within 1 week, then the dose should be skipped and resumption of the elotuzumab continues per the protocol defined schedule.

4.5.3.2 *Dexamethasone*

Dexamethasone delay should be performed as clinically indicated at the discretion of the investigator.

For subjects receiving elotuzumab, the weekly dexamethasone dose that coincides with or is temporally closest to the elotuzumab dosing must be administered as part of the premedication for elotuzumab per the guidance in [Section 4.5.1](#).

4.5.3.3 *Lenalidomide*

Lenalidomide delay should be performed as clinically indicated at the discretion of the investigator.

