7.4.1.1 Duration of Study Therapy

The number of cycles of treatment received by subjects will be summarized (using n, mean, STD, median, min, max, q1 and q3) by treatment group. A summary of the number of subjects taking each drug in each cycle will also be presented by treatment group.

The duration of each treatment (elotuzumab, dexamethasone [oral, IV, and oral and IV combined] and lenalidomide), in months, will be calculated as:

$$(date\ of\ last\ dose\ of\ the\ drug - date\ of\ first\ dose\ of\ the\ drug + 1) / 30.4375$$

Duration of each of the study treatments will be summarized by treatment group.

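### SAP 7.4.4 tabulates single-drug discontinuation for ELd only, so the frequency of and reasons for stopping lenalidomide or dexamethasone alone cannot be compared directly between arms

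*SAP*

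**What the plan says.** SAP 7.4.4 describes two summaries.

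- Whole-regimen discontinuation, in both arms: "The number and percentage of subjects who have discontinued all study treatment and reason for discontinuation will be summarized by treatment group and overall". It takes the reason from the end-of-treatment status page and includes all randomized subjects.
- Single-drug discontinuation, in one arm: reasons are summarized from the dose modification page "for subjects in the Elotuzumab arm, who discontinued one drug, while continuing at least one of the other two study drugs". A subject qualifies if the dosing page shows the combination in at least one cycle and then further cycles with one of the drugs stopped.

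Protocol 4.5.3 allows partial discontinuation without naming an arm: "Subjects may continue on study therapy even if components of the study therapy must be discontinued". Its first example is the two-drug regimen: "a subject on lenalidomide and dexamethasone may continue on study therapy even if dexamethasone must be discontinued for an adverse event". It closes with: "Patients are considered still on study therapy even if they continue solely on lenalidomide".

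Protocol 3.5 lists lenalidomide-related skin reactions and angioedema after which lenalidomide must stop. There it adds: "Subjects in the elotuzumab arm may continue elotuzumab and dexamethasone". It has no matching sentence for control subjects.

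SAP 5 says that results from both arms will help assess what elotuzumab adds to Ld, and that no formal comparison between arms is planned.

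**The concern.** Lenalidomide and dexamethasone are common to both arms. Whether adding elotuzumab leads more subjects to give up one of them, and for what reasons, is a natural descriptive question for a randomized trial, and the dosing data to answer it are collected. As SAP 7.4.4 is written, single-drug stops and their reasons are tabulated for ELd with no control column beside them. A reader of the report would see, for example, the ELd subjects who stopped dexamethasone alone, and could not tell whether the number and the reasons were usual for Ld treatment. No reason for the one-arm restriction is given.

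**Working it through.** The plan states no figure on this point, so the check is mainly a comparison of texts.

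**Step 1. Follow the same event in each arm.** A subject stops dexamethasone for an adverse event and continues lenalidomide.

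| SAP 7.4.4 summary | ELd subject | Ld subject |
|---|---|---|
| All study treatment stopped (both arms) | Not counted while another drug continues | Not counted while lenalidomide continues (Protocol 4.5.3) |
| One drug stopped, another continued (ELd only) | Counted, with reason | Not eligible |

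If the Ld subject later stops lenalidomide too, the first summary picks the subject up, but with the end-of-treatment reason. The dexamethasone stop is still not tabulated as such.

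**Step 2. Look for the missing cell elsewhere in the SAP.**

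- 7.4.1.1, per-cycle counts: "A summary of the number of subjects taking each drug in each cycle will also be presented by treatment group". In any cycle, subjects on lenalidomide minus subjects on dexamethasone equals those on lenalidomide without dexamethasone minus those on dexamethasone without lenalidomide. That is a net number. It mixes skipped doses with permanent stops and carries no reasons.
- 7.4.1.1, drug duration, by arm: last dose minus first dose plus 1 day. Dexamethasone duration is the same whether the subject stopped dexamethasone alone or everything on that day.
- 7.4.1.2, lenalidomide: reductions are by arm and concern dose level. An interruption needs a gap between two dosing dates within a cycle, so a permanent stop, with no later dosing date, does not meet the definition.
- 7.4.1.2, oral dexamethasone: modifications are listed with reasons. The text does not say that they are shown by arm or that a permanent stop counts as a modification.
- 7.4.1.3: cumulative dose and dose intensity, by arm, without reasons.
- 7.6.2: adverse events leading to discontinuation. The text does not say that they are split by drug, or whether single-drug stops count.

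**Step 3. Test whether dose intensity would reveal a permanent stop.** Suppose, for illustration, that a control subject takes full doses on schedule through Cycle 2 and then stops one drug for good. Read the last cycle in the SAP formulas as the last cycle in which that drug was given.

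- Dexamethasone, Cycles 1 and 2: cumulative dose 2 × 4 × 40 = 320 mg; denominator 28 + 28 = 56 days; intensity 7 × 320 / 56 = 40 mg/week. The planned control figure is 40 mg/week, so relative dose intensity is 100%. The subject has no dexamethasone dose in Cycles 3 to 18 and so no first dose date for that formula.
- Lenalidomide: cumulative dose 2 × 21 × 25 = 1,050 mg; denominator 56 days; intensity 7 × 1,050 / 56 = 131.25 mg/week, which is the SAP's planned figure. Relative dose intensity is again 100%.

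Time after the stop largely falls outside the denominator, so dose intensity hardly registers this event. Cumulative dose does fall, but equally for a whole-regimen stop at the same time.

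**Step 4. How precise would the missing comparison be?** The documents give no rates, so these are assumptions, with 40 subjects per arm. The 95% half-width for a difference is 1.96 × √[p₁(1 − p₁)/40 + p₂(1 − p₂)/40].

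| Assumed rates | Difference | Half-width |
|---|---|---|
| 5% and 10% | 5 points | 11.5 points |
| 10% and 20% | 10 points | 15.5 points |
| 20% and 40% | 20 points | 19.6 points |

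The table would be descriptive and could show only large differences.

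**The case against.** The strongest reply is that SAP 7.4.4 should not be read alone. The SAP reports the shared drugs by arm in several places, and an Ld subject who stops dexamethasone does leave the per-cycle dexamethasone count and does have a shorter dexamethasone duration. This stands. A reader might infer that the effect of elotuzumab on tolerance of the shared drugs cannot be read at all, or that partial discontinuations in Ld vanish from the report. The documents support neither. What is missing is the direct tabulation with reasons.

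A second reply is that the control arm is there for add-on efficacy (Protocol 8.1, SAP 5), that the visible objectives are ORR and PFS, and that no formal comparison is planned. It stands in that no stated objective is defeated. It does not justify a one-arm table, because the proposed table is also descriptive and SAP 5 wants both arms to inform the effect of adding elotuzumab.

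A third reply concerns lenalidomide. A reader might take a control subject's stopping lenalidomide alone to be as well established as stopping dexamethasone alone. It is not: it rests on the general sentence in Protocol 4.5.3, while Protocol 3.5 spells out continuation for the elotuzumab arm only.

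Finally, a reader might infer that the ELd summary will merge elotuzumab stops with stops of the shared drugs. SAP 7.4.4 neither requires nor excludes rows by drug, so that would be an argument from silence.

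**Conclusion.** The point holds as a narrow reporting gap. The SAP specifies the number of and reasons for single-drug discontinuation in ELd only, and no other planned output clearly supplies them for Ld. The indirect by-arm tables lack reasons and do not isolate single-drug permanent stops.

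The size cannot be stated. The number of control subjects affected may be anything from none to all of the roughly 40, and the documents give no rate. The conclusion assumes that the SAP text governs the tables produced and that control subjects do sometimes stop one drug alone, as Protocol 4.5.3 allows explicitly for dexamethasone. The dose-intensity argument also assumes the reading of the last cycle given above.

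This is a low-priority improvement. The sample size, the decision rule of 32 responders out of 40, and the ORR and PFS analyses are untouched.

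**What to change.** In SAP 7.4.4, replace the ELd-only summary with wording such as: *For each study drug, the number and percentage of subjects who permanently discontinued that drug while continuing at least one other study drug will be presented by treatment group, with the reason. Lenalidomide and dexamethasone rows will be shown for both arms and the elotuzumab row for ELd only.* State the denominator for the percentages.

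The existing counting rule carries over, with the combination meaning two drugs in Ld and three in ELd. The sources are the dosing and dose modification CRF pages already named in the section. The cost is one extended table, with no new data collection.

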7.4.5 Subsequent Anti-Myeloma Therapy

A by-subject listing of all subsequent surgery, all subsequent radiation therapy, and all subsequent systemic anti-myeloma therapy will be provided using the BMS WHO drug dictionary.

7.5 Efficacy

Efficacy analyses (ORR and PFS) will be conducted on the population of all randomized subjects. All analyses of ORR and PFS will be based on the investigator evaluation. Unless stated otherwise, whenever a stratified analysis is specified, the stratifications factor will be those used in the randomization, that is:

- Stage of disease (ISS 1 – 2 versus 3)

CI's will be at the two-sided 70% level and at the two-sided 95% level for ORR analysis as primary endpoint, and the other analyses, respectively.

7.5.1 Analyses of Objective Response

Analysis for Primary objective:

The response rate and its corresponding exact two-sided 70% confidence interval (Clopper and Pearson¹⁹) will be calculated in the ELd arm.

The number and percentage of subjects in each category of best overall response per Investigator (complete response [CR], and whether CR was stringent CR [sCR], PR and whether PR was very good partial response [VGPR], stable disease [SD], progressive disease [PD], or unable to determine [UD]) will be presented, by treatment group.

Analysis for Secondary objective:

An estimate of the response rate and an associated exact two-sided 95% CI will be presented, by treatment group.

The difference in ORR between two treatment arms along with two-sided 95% CI will be estimated using the method of DerSimonian and Laird adjusted by stage of disease (ISS stage 1- 2 versus 3). In addition, the response rate and its corresponding exact two-sided 95% confidence interval will be calculated in both arms.

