Secondary Endpoints:

The difference in ORR between two treatment arms along with two-sided 95% CI will be estimated using the method of DerSimonian and Laird adjusted by stage of disease (ISS stage 1 - 2 versus 3). In addition, the response rate and its corresponding exact two-sided 95% confidence interval will be calculated in the Ld arm.

The PFS analyses will be conducted using both the primary and the ITT definitions of PFS. The PFS functions for each randomized arm will be estimated using the Kaplan-Meier product-limit method. Two-sided, 95% confidence intervals for median PFS and the first and third quartiles will be computed by treatment arm. PFS rates at 1, 2, and 3 years will be estimated from the KM curve. Each analysis will be performed after all subjects have been followed for the appropriate time.

TABLE OF CONTENTS

TITLE PAGE	1
DOCUMENT HISTORY	3
SYNOPSIS.....	4
TABLE OF CONTENTS.....	8
1 INTRODUCTION AND STUDY RATIONALE	12
1.1 Study Rationale.....	12
1.1.1 Unmet Medical Needs in Multiple Myeloma	12
1.1.2 Non-clinical Rationale for Elotuzumab in Combination with Lenalidomide and Dexamethasone	12
1.1.2.1 Elotuzumab	12
1.1.2.2 Combination of Elotuzumab with Lenalidomide/dexamethasone...	13
1.2 Research Hypothesis.....	14
1.3 Objectives(s)	14
1.3.1 Primary Objectives	14
1.3.2 Secondary Objectives	14
1.3.3 Exploratory Objectives	14
1.4 Product Development Background.....	14
1.4.1 Non-clinical Toxicology	14
1.4.2 Clinical Experience with Elotuzumab in Multiple Myeloma	15
1.4.2.1 Non-Japanese Clinical Study Results	15
1.4.2.2 Japanese Clinical Trial Results	19
1.4.2.3 Infusion Reactions	20
1.4.2.4 Clinical Pharmacokinetics	21
1.4.3 Rationale of Selection of Dosage and Administration in this Study	22
1.4.3.1 Elotuzumab Dosing	22
1.4.3.2 Elotuzumab Infusion Rate	25
1.4.4 Rationale for Study Design	27
1.4.4.1 Rationale for Treating with Ld Until Progression	27
1.4.4.2 Population of Untreated Subjects Ineligible for SCT	29
1.4.5 Rationale for Inclusion of Subjects with Mild to Moderate Renal Impairment	29
1.5 Overall Risk/Benefit Assessment	30
2 ETHICAL CONSIDERATIONS.....	31
2.1 Good Clinical Practice	31
2.2 Institutional Review Board	32
2.3 Informed Consent.....	32
3 INVESTIGATIONAL PLAN.....	33
3.1 Study Design and Duration.....	33
3.2 Post Study Access to Study.....	34
3.3 Study Population.....	35

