3.1 Study Design and Duration

This is a Phase 2, randomized, open-label, multi-center trial investigating lenalidomide/dexamethasone with and without elotuzumab in subjects with newly diagnosed, previously untreated multiple myeloma who are ineligible for high-dose therapy plus stem-cell transplantation (SCT) because of age (≥ 65 years) or coexisting conditions.

Eligible subjects will be randomized in a 1:1 ratio to receive either elotuzumab/lenalidomide/dexamethasone (ELd) [Investigational Arm] or lenalidomide/dexamethasone (Ld) [Control Arm]. The randomization will be stratified by International Staging System (ISS) stage (1 - 2 versus 3). Approximately eighty subjects in total will be randomized to either arm.

The study design schematic is presented in [Figure 3.1-1](#).

Figure 3.1-1: Study Design Schematic

A cycle is defined as 28 days. Treatment with study drug continues until disease progression (PD), unacceptable toxicity or subject meets other criteria for discontinuation of study drug outlined in [Section 3.5](#).

Disease assessments, based on the IMWG response criteria, will be conducted every 4 weeks relative to the first dose of study medication until disease progression. Response and progression assessment will be investigator-based and no central lab or independent review is planned.

For the subject who does not have documented disease progression at time of study drug discontinuation, tumor assessments should still be performed according to the same schedule until disease progression even if a subsequent anti-myeloma treatment is initiated prior to disease progression.

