8.4.2.2 Secondary Efficacy Analysis

The difference in ORR between two treatment arms along with two-sided 95% CI will be estimated using the method of DerSimonian and Laird adjusted by stage of disease (ISS stage 1- 2 versus 3). In addition, the response rate and its corresponding exact two-sided 95% confidence interval will be calculated in the Ld arm.

The PFS analyses will be conducted using both the primary and the ITT definitions of PFS. The PFS functions for each randomized arm will be estimated using the Kaplan-Meier product limit method. Two-sided, 95% confidence intervals for median PFS and the first and third quartiles will be computed by treatment arm. PFS rates at 1, and 2 years will be estimated from the KM curve. Each analysis will be performed after all subjects have been followed for the appropriate time.

[REDACTED]

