8.5 Interim Analyses

The primary analysis will be done 6 months after last subject's first treatment. Additional analyses may be performed which depend on the timing of regulatory authority filing. The final analysis may be performed at the timing of the study discontinuation.

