5 SAMPLE SIZE AND POWER

The number of subjects in the investigational arm (ELd arm) is based on the primary objective of assessment in objective response rate in ELd arm. The design will test the null hypothesis that the response rate $\leq 71\%$ versus the alternative that the true response rate $> 71\%$. The test will have a significance level of 15% (one-sided) and will have 80% power to reject the null hypothesis if the true response rate is 85%. If there are 32 or more responders out of 40 subjects in the ELd arm, the null hypothesis will be rejected. The study design requires 40 subjects in ELd arm.

The control arm (Ld arm) is designed to evaluate add-on efficacy clinically for Elotuzumab with 40 subjects. The randomized ratio of ELd to Ld is 1:1.

This is a randomized study and the results from both treatment arms will help assess the effect of elotuzumab addition to Ld in the treatment of Japanese subjects with newly diagnosed MM, and put into the right perspective. However, no formal comparisons between treatment arms are planned since a formal comparative study would require a prohibitively large sample size. The efficacy of adding elotuzumab to Ld therapy in the treatment of subjects with newly diagnosed, previously untreated MM will be confirmed on the basis of the large global pivotal study CA204-006, results of which will be used in conjunction with results from the current study to support the JNDA submission.

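### Minor: the ELd−Ld difference in ORR is pooled over two fixed ISS strata with a DerSimonian-Laird random-effects model; the interval is valid but unstable, and on average 19-24% wider than a stratified Newcombe interval

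*SAP*

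**What the plan says.** Estimating the ORR difference between ELd and Ld is a secondary objective (protocol 1.3.2). SAP 7.5.1 specifies: "The difference in ORR between two treatment arms along with two-sided 95% CI will be estimated using the method of DerSimonian and Laird". The pooling there is over two ISS groups, 1-2 and 3. Protocol 8.4.2.2 agrees ("estimated using the method of DerSimonian and Laird adjusted by stage of disease"), as does the protocol synopsis, so the documents are consistent. SAP 7.5 adds that "whenever a stratified analysis is specified, the stratifications factor will be those used in the randomization", which confirms that the two ISS groups are the randomization strata.

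The available text gives no reason for a random-effects model, no rule for strata with an empty cell, and no sensitivity method. For PFS, SAP 7.5.2 treats the same factor conventionally: a Cox model stratified by ISS with a single treatment effect.

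SAP 5 limits the role of the comparison: "no formal comparisons between treatment arms are planned since a formal comparative study would require a prohibitively large sample size".

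**The concern.** DerSimonian-Laird (DL) was built for pooling studies regarded as draws from a wider population. Here there are exactly two strata, fixed by design, in one trial. The between-stratum variance is estimated from a single contrast of two stratum differences, and the ISS 3 stratum may hold only 8-14 subjects per arm. When that estimate is zero, DL is the inverse-variance fixed-effect interval. When it is positive by chance, the interval widens sharply and the weights shift towards the small stratum.

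At stake is the precision and stability of a descriptive estimate. Its width, and to a lesser extent its centre, can turn on which stratum one responder belongs to while both arm totals stay the same. Validity is not at stake, and neither is any decision rule.

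**Working it through.** **The plan's own figure.** No precision is stated for the difference. The stated ELd rule reproduces: at least 32 of 40 has exact one-sided error 0.139 at 71% (a cut-off of 31 gives 0.236) and exact power 0.865 at 85%. It uses the ELd arm alone, so the choice of DL does not touch it.

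**Inputs from the documents.** 40 per arm, 1:1 allocation, two strata, two-sided 95% CI; 85% is the ELd design alternative (SAP 5).

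**Assumptions.** Ld rate 71% (in the documents this is only the null value for ELd); the same true effect in both strata; ISS 3 share 20, 25, 30 or 35%, i.e. 8, 10, 12 or 14 per arm; 0.5 added only in strata with an empty cell.

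**Formulas.** For stratum i, d_i is the difference in response rates, v_i = p_E(1−p_E)/n + p_L(1−p_L)/n, and w_i = 1/v_i. With μ = Σw_i d_i / Σw_i:

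- Q = Σw_i(d_i − μ)² and C = Σw_i − Σw_i²/Σw_i
- τ² = max{0, (Q − 1)/C}
- DL weights 1/(v_i + τ²); SE = 1/√Σ[1/(v_i + τ²)]; width = 2 × 1.96 × SE

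The comparator is the Mantel-Haenszel (MH) weighted difference, with limits that combine the Wilson-based Newcombe limits of each stratum using the MH weights.

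**One worked pair.** Totals are 34/40 versus 28/40, with 10 ISS 3 subjects per arm and no empty cells. The pair was chosen to illustrate.

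1. ISS 1-2 25/30 vs 22/30; ISS 3 9/10 vs 6/10. d = 0.100 and 0.300; v = 0.01115 and 0.03300; Q = 0.906 < 1, so τ² = 0. DL: 15.1 points (−2.8 to 32.9), width 35.8. Newcombe: 15.0 (−3.4 to 31.8), width 35.2.
2. Move one Ld responder from ISS 3 to ISS 1-2: 25/30 vs 23/30; 9/10 vs 5/10. d = 0.067 and 0.400; v = 0.01059 and 0.03400; Q = 2.492; C = 44.85; τ² = 1.492/44.85 = 0.0333. Weights go from 94.4 and 29.4 to 22.8 and 14.9; SE = 0.163. DL: 19.8 points (−12.1 to 51.8), width 63.9. Newcombe: 15.0 (−3.3 to 31.5), width 34.8.

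**Exact enumeration of all outcomes, 85% versus 71%:**

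| ISS 3 per arm | 8 | 10 | 12 | 14 |
|---|---|---|---|---|
| P(τ² > 0) | 0.320 | 0.326 | 0.324 | 0.330 |
| Mean width, DL (points) | 43.2 | 42.4 | 41.7 | 41.2 |
| Mean width, Newcombe | 34.7 | 34.7 | 34.7 | 34.7 |
| Median width, DL | 36.3 | 36.3 | 36.3 | 36.3 |
| Median width, Newcombe | 34.9 | 34.9 | 34.8 | 34.8 |
| 95th percentile, DL | 83.3 | 77.7 | 74.4 | 72.7 |
| 95th percentile, Newcombe | 37.4 | 37.3 | 37.2 | 37.2 |
| P(DL width > 50) | 0.209 | 0.192 | 0.182 | 0.173 |
| Coverage, DL | 0.957 | 0.954 | 0.955 | 0.954 |
| Coverage, Newcombe | 0.951 | 0.952 | 0.953 | 0.952 |

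The Newcombe width never exceeds about 40 points. Given τ² > 0, DL is on average 1.6-1.8 times as wide as the fixed-effect interval. Over all trials the ratio is at least 1.6 in 14-17%.

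**Stability.** Moving one responder at random between strata, arm totals unchanged, changes the DL width by 25% or more in 37-43% of cases and by 50% or more in 12-27%. The Newcombe width changes by at most about 9%.

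**Sensitivity.**

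- ISS 3 share 10-50%: DL mean 41-46 points.
- Ld rate 60-80%: DL 14-28% wider on average.
- Other empty-cell conventions: DL mean 39.7-44.6.
- Unequal stratum effects (87% vs 75% in ISS 1-2; 79% vs 60% in ISS 3): DL 43.4-45.4 vs Newcombe 33.9-34.6, with Newcombe coverage about 95%.

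**The case against.** DL is named in advance, stated identically in three places and has nominal coverage, so replacing it exchanges one valid interval for another. No decision depends on it: no formal comparison is planned, and exact 95% CIs for each arm are reported anyway. The mean exaggerates the typical penalty. In the two thirds of trials with τ² = 0, DL averages about 34.7 points; the median penalty is about 1.5 points; and DL is the narrower interval in 35-36% of trials (56% if the Ld rate is 80%). The point estimate itself loses little: its root mean squared error is 0.092-0.097 for DL against 0.091 for MH. Every figure depends on an Ld rate, an ISS 3 share and an empty-cell rule that the documents do not give. Stratified Newcombe also has more than one form.

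All of this is accurate, and it sets the grade at minor. It does not remove the point. The direction holds across every range tried, including the empty-cell conventions. The two Newcombe forms differ by less than one point (34.7 versus 35.3-35.4). Allowing real differences between strata leaves DL wider. What remains is a long upper tail that arises by chance and has no design purpose. Two parts of the objection should be acted on: the SAP needs an empty-cell rule if DL is kept in any role, and the replacement must name one form of the Newcombe interval.

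**Conclusion.** The concern holds as a cheap improvement; the plan is not in error. With 40 per arm, 85% versus 71%, equal stratum effects, an ISS 3 share of 20-35% and 0.5 added in strata with an empty cell, the DL interval averages 41-43 points against 34.7, which is 19-24% wider. The excess is concentrated: about one trial in five or six gives a DL interval wider than 50 points, and the MH/stratified Newcombe interval never does. Coverage is 95.4-95.7% and 95.1-95.3% respectively. The exact sizes rest on the assumed inputs; the direction of the mean and the instability do not.

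**What to change.** **If ORR has not yet been analysed**, revise the protocol synopsis, protocol 8.4.2.2 and SAP 7.5.1 to read:

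> The difference in ORR (ELd minus Ld) will be estimated as the Mantel-Haenszel-weighted risk difference stratified by ISS stage (1-2 versus 3), with a stratified Newcombe two-sided 95% CI obtained by combining the stratum-specific Newcombe (Wilson-based) limits with the Mantel-Haenszel weights. The DerSimonian-Laird estimate will be reported as a sensitivity analysis, adding 0.5 to each cell of any stratum that has an empty cell.

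Do not use the fixed-effect Wald interval instead: it covers about 94% under the same assumptions.

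**If ORR has already been analysed**, keep the prespecified DL result as the reported estimate, state the empty-cell rule that was used, and show MH/stratified Newcombe beside it as a labelled sensitivity analysis.

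The fix is conditional because protocol 8.5 says "The primary analysis will be done 6 months after last" subject's first treatment, and the documents do not show whether that date has passed. Protocol 3.1 describes the study thus: "This is a Phase 2, randomized, open-label, multi-center trial". Responses are investigator-assessed, so replacing the estimator once they are visible would cost credibility.

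**Cost.** Wording in three places and one extra table row; no new data and no effect on the primary analysis or sample size. The remaining downside is departing from a prespecified method that the sponsor may also use in other studies.
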